9.2 Methods for Evaluation

All baseline evaluations will be performed as closely as possible to the beginning of treatment. Please refer to the study calendar and Section 3 (study design).

Physical Examination, Laboratory Values, Food Records

After completing a dietary assessment, patients will undergo physical examination and laboratory tests (complete blood count (CBC) with differential, platelet count, and serum chemistry assessment). The treating physician will evaluate the patient every cycle. Peripheral blood samples will be collected cycles 1–4, 7, 10, and EOT for evaluation of methylation status.

9.3 Surrogate Endpoint Biomarkers

Plasma uptake and urine excretion of berry anthocyanins

We will evaluate the uptake of berry compounds into plasma obtained at two hours after the first dose of BRBs. Urine samples will also be collected three hours after the first dose of BRBs. The content of each of the four major anthocyanins in BRBs (i.e., cyanidin-3-rutinoside, cyanidin-3-sylosylrutinoside, cyanidin-3-glucoside and cyanidin-3-sambubioside) will be measured, using HPLC, as described previously. (17) Briefly, separation of plasma and urinary anthocyanins will be conducted on a Symmetry C18 column ($4.6 \times 75 \text{ mm}$, $3.5 \mu \text{m}$; Waters Corp.) using an HPLC system. Cyanidin-3-glucoside will be dissolved in deionized-distilled water containing 5% formic acid. All levels of anthocyanins analyzed in plasma and urine samples will fall within the standard curve range and will be expressed as cyanidin glucoside equivalents in pmol/mL plasma or urine.

DNA methylation analysis by reduced representation bisulfite sequencing (RRBS)

Peripheral blood will be used to isolate CD45+ leukocytes, using CD45 MicroBeads (Miltenyi Biotec). DNA will be extracted from isolated leukocytes (DNA extraction kit, Qiagen). Then, DNA samples will be used for RRBS analysis. In brief, first, genomic DNA is digested using a methylation-insensitive restriction enzyme. The next step is adding an extra adenosine to both the plus and minus strands. End repair and A-Tailing is done within the same reactions, with dCTP, dGTP and dATP deoxyribonucleotides. Then, methylated sequence adapters are ligated to the DNA fragments. The desired size of fragments is then selected to be purified. DNA fragments of 40-220 base pair are representative of the majority of promoter sequences and CpG islands. The DNA fragments are then bisulfite converted, which is a process that deaminates unmethylated cytosine into a uracil. The methylated cytosine remains unchanged, due to the methyl group protecting them from the reaction. The bisulfite converted DNA is then amplified, using PCR with primers that are complementary to the sequence adapters. The fragments are then sequenced. For Illumina sequencing, 36-base single-end sequencing reads are most commonly performed. Alignment to a reference genome allows the programs to identify base pairs within the genome that are methylated. The identified genes will be validated using pyrosequencing.

The research samples will be batched and any leftover blood/urine will be banked for future research. The research samples will be processed and banked at [name] lab at the R4655 TBRC, Medical College of Wisconsin, [name].

9.4 Response Criteria

The patient's best clinical response will be assessed, based on the modified IWG response criteria (Appendix 2) while receiving BRBs.

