2.2 Secondary Objectives

- 1. To evaluate the toxicity of BRBs in patients with MDS or MDS/MPN.
- 2. To evaluate the hematological response according to modified IWG criteria (Appendix 2) in patients with MDS or MDS/MPN regardless of the initial blood count.
- 3. To evaluate the anthocyanin concentrations in peripheral blood of patients prior to and after administration of BRB powder on Cycle 1 Day 1 of treatment.

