3 STUDY DESIGN

3.1 General Description

This is a phase II single-group pilot study. This trial is designed to evaluate efficacy and methylation. This study's overarching aim is to evaluate the systemic effects of BRBs in patients with MDS or MDS/MPN. Eighteen patients with MDS or MDS/MPN will be treated with 25 gm (2x/day) of BRB powder taken orally in 8 ounces of water. If the patient is unable to tolerate the taste of the BRB powder mixed in water, he or she may mix it with 8 ounces of milk, ice cream or a smoothie.

Anthocyanins in the blood will be measured within three hours prior to BRB administration, and two hours (+/- 30 minutes) after the first dose. Urine anthocyanins will be measured within three hours prior to BRB administration and three hours (+/-30 minutes) after the first BRB dose. Both of those time points were chosen based on previous studies demonstrating that the maximum concentrations of anthocyanins and ellagic acid in plasma occurred at one to two hours, and maximum quantities in urine appeared from zero to four hours. (20) Methylation status will be measured within three hours prior to BRB administration in cycles 1–4, 7, 10 and at the end of treatment visit.

Patients will receive oral BRBs while receiving their supportive care for a period of at least three cycles. At cycles 4 and 7, day 1, the patient will be assessed for response (Appendix 2) and toxicity. If the patient is tolerating BRBs well and is benefiting from therapy, he or she will continue treatment for a total maximum of 12 cycles. Tolerating well is defined as no grade 3 or 4 toxicity.

*Benefiting from therapy (for cycle 3 disease assessment) defined as CR, PR, HI, stable disease with no disease progression (see Appendix 2).

**Benefiting from therapy (for cycle 6 disease assessment) defined as CR, PR or HI (see Appendix 2).

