4.1 Inclusion Criteria

A potential subject must meet all the following inclusion criteria to be eligible to participate in the study.

1. Patients must have a confirmed diagnosis of myelodysplastic syndrome or myelodysplastic syndrome/ myeloproliferative neoplasms (MDS/MPN) proven by bone marrow biopsy/aspirate.

- 2. Patients with cytopenias (blood cell counts lower than the institutional lower limit of normal within the eight weeks prior to the study) who are receiving or received:
 - red blood cell transfusions
 - observation
 - platelet transfusions
 - erythropoietin
 - granulocyte colony-stimulating factors
 - granulocyte-macrophage colony-stimulating factors
 - hydrea
- 3. Age >18 years.
- 4. Predicted life expectancy of at least 12 weeks.
- 5. Patients should be expected to stay on the same therapy for the period of the study.
- 6. Patients who do not have an indication for and/or are believed to be unable to tolerate a hypomethylating agent are eligible for the study.
- 7. Reproductive requirements:

Female patients must meet one of the following:

- Postmenopausal for at least one year before the screening visit, or
- Surgically sterile, or
- If they are of childbearing potential, agree to practice two effective methods of contraception from the time of signing of the informed consent form through 30 days after the last dose of study drug, AND
- Must also adhere to the guidelines of any treatment-specific pregnancy prevention program, if applicable, or
- Agree to practice true abstinence when this is in line with the preferred and usual lifestyle of the subject. (Periodic abstinence [e.g., calendar, ovulation, symptothermal, postovulation methods] and withdrawal are not acceptable contraception methods.)

Male patients, even if surgically sterilized (i.e., status postvasectomy), must agree to one of the following:

- Practice effective barrier contraception during the entire study treatment period and through 30 days after the last study drug dose, OR
- Must also adhere to the guidelines of any treatment-specific pregnancy prevention program, if applicable, OR
- Agree to practice true abstinence when this is in line with the preferred and usual lifestyle of the subject. (Periodic abstinence [e.g., calendar, ovulation, symptothermal, postovulation methods] and withdrawal are not acceptable methods of contraception.)
- 8. Ability to understand a written informed consent document, and the willingness to signit.

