6.3 General Concomitant Medication and Supportive Care Guidelines

The treating physician will use standard supportive care to control symptoms and improve quality of life. These may include:

- Transfusions
- Use of growth factors
- Antibiotics

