6.5 Prohibited Medications

As noted in the eligibility section 4, patients should not be receiving hypomethylating agents. In addition, they should not be receiving other chemotherapy/radiation, or participating in clinical trials with other investigational agents not included in this trial, within 14 days of the start of this trial and throughout the duration of this trial.

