APPENDIX 2. MODIFIED IWG RESPONSE CRITERIA

Hematologic	Response Criteria (responses must last at least 8 weeks)				
Improvement (HI)					
Erythroid response	- Hgb increase by ≥ 1.5 g/dL.				
(pretreatment, < 11 a/dL)	- Relevant reduction of RBC transfusion units by an absolute				
. ,	number of at least 4 RBC transfusions/8 wk compared with				
	the pretreatment transfusion number in the previous 8 wk.				
	- Only RBC transfusions given for an Hgb of \leq 9.0 g/dL				
	pretreatment will count in the RBC transfusion response				
	evaluation.				
Platelet response	- Absolute increase of \geq 30 x 109/L for patients starting with				
(pretreatment, < 100 x 109/L)	> 20 x 109/L platelet.				
	- Increase from < 20 x 109/L to > 20 x 109/L and by at least				
	100%.				
Neutrophil	At least 100% increase and an absolute increase > 0.5 x 109/L.				
response (pretreatment					
< 1.0 x 109/L)					
Progression or	At least one of the following:				
relapse after HI	- At least 50% decrement from maximum response levels in				
	aranulocytes or platelets				
	= Reduction in Hab by > 1.5 a/dl				
	- Reduction in rigb by ≥ 1.5 g/dE.				
	- i ransiusion dependence in transfusion independent				
	patients.				

Category	Response criteria (responses must last at least 4 weeks)
Complete remission	Bone marrow: ≤ 5% myeloblasts with normal maturation of all cell lines Persistent dysplasia will be noted
	Peripheral blood: Hgb \geq 11 g/dL Platelets \geq 100 × 10 ⁹ /L Neutrophils \geq 1.0 × 10 ⁹ /L Blasts 0%
Partial remission	All CR criteria if abnormal before treatment except: Bone marrow blasts decreased by ≥ 50% over pretreatment but still > 5% Cellularity and morphology not relevant
Marrow CR	Bone marrow: $\leq 5\%$ myeloblasts and decrease by $\geq 50\%$ over pretreatment
	Peripheral blood: if HI responses, they will be noted in addition to marrow CR
Stable disease	Failure to achieve at least PR, but no evidence of progression for > 8 weeks.
Failure	Death during treatment or disease progression characterized by worsening of cytopenias, increase in percentage of bone marrow blasts, or progression to a more advanced MDS FAB subtype than pretreatment
Cytogenetic response	Complete: Disappearance of the chromosomal abnormality without appearance of new ones Partial: At least 50% reduction of the chromosomal abnormality

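### Hematologic improvement on BRB is scored with no rule for growth factors started or increased on study (or hydrea reduced), so a response they drive would be credited to BRB

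*Combined protocol and SAP*

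**What the plan says.** Response is a secondary endpoint (Section 3.4), and Section 9.4 gives the scoring rule: "The patient's best clinical response will be assessed, based on the modified IWG response criteria (Appendix 2) while receiving BRBs". Section 2.2 adds that it is evaluated "in patients with MDS or MDS/MPN regardless of the initial blood count".

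The HI table in Appendix 2 carries the header "Response Criteria (responses must last at least 8 weeks". It sets a pretreatment level and a size of change for each lineage:

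- Erythroid: hemoglobin below 11 g/dL, then a rise of at least 1.5 g/dL or at least 4 fewer red cell units per 8 weeks.
- Platelets: below 100 × 10⁹/L, then a rise of at least 30 × 10⁹/L, or a doubling to above 20 × 10⁹/L for those starting below that level.
- Neutrophils: below 1.0 × 10⁹/L, then a doubling with an absolute gain above 0.5 × 10⁹/L.

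On background treatment, Section 3.1 states: "Patients will receive oral BRBs while receiving their supportive care for a period of at least three cycles". Section 6.3 states: "The treating physician will use standard supportive care to control symptoms and improve quality of life. These may include", and its list includes transfusions and "Use of growth factors". Section 6.5 rules out hypomethylating agents and continues: "In addition, they should not be receiving other chemotherapy/radiation, or participating in clinical trials with other investigational agents". It names neither growth factors nor transfusions.

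In Section 4.1, criterion 2 admits patients on observation, transfusions, erythropoietin, G-CSF, GM-CSF or hydrea. Criterion 5 reads: "Patients should be expected to stay on the same therapy for the period of the study". Section 10 has no analysis text for hematologic response.

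**The concern.** Erythropoietin, G-CSF and GM-CSF are given to raise the counts that define HI, and a lower hydrea dose can let counts recover. If one of these changes during treatment and the patient then meets Appendix 2, the scoring rule records a response on BRB. No control arm shows how often this happens without BRB, and no passage says how such a response is classified. The error runs one way: it can add responders but cannot remove them.

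At stake is the only clinical efficacy signal in the trial. There is also a small knock-on: HI counts as benefit at the cycle 7 assessment, so it helps decide who stays on BRB.

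**Working it through.** **1. The plan's own figure.** The plan gives no target rate, test or power for response. Its one design calculation is for methylation: a two-sided paired t-test, alpha 0.05/24 = 0.00208, difference 12, SD 8. Recomputed with the noncentral t, 16 patients give 97.3% power, which meets the stated 95%. Then 16 × 1.05 × 1.05 = 17.6, which rounds up to 18. None of this depends on the response rule.

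**2. Following the rule for one patient.** A patient enters on observation with hemoglobin below 11 g/dL and starts erythropoietin during cycle 1. Hemoglobin rises by 1.5 g/dL and holds for 8 weeks.

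- Section 6.3 permits the treatment, and Section 6.5 does not exclude it.
- Criterion 5 was met if stable therapy was expected at entry.
- Appendix 2 is satisfied on baseline level, size and duration.
- Section 9.4 asks only that the patient was receiving BRB.

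The patient is scored as an HI responder.

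**3. Whether the 8-week rule prevents this.** Response is assessed on treatment at day 1 of cycles 4 and 7. These fall 3 × 28 = 84 days (12 weeks) and 6 × 28 = 168 days (24 weeks) after day 1. If the 8 weeks must be complete by the assessment (the plan does not say), a rise beginning by week 12 − 8 = 4 or week 24 − 8 = 16 qualifies. A continued growth factor can sustain a rise that long.

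**4. Size.** The documents give no rate of growth-factor initiation and no HI rate from supportive care, so the rate q is an assumption, shown over a range. With n = 18, one misattributed HI adds 1/18 = 5.6 points. Exact 95% intervals:

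| Responders | Rate | 95% CI |
|---|---|---|
| 0/18 | 0% | 0 to 18.5% |
| 1/18 | 5.6% | 0.1 to 27.3% |
| 2/18 | 11.1% | 1.4 to 34.7% |

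The chance of at least one such HI is 1 − (1 − q)ⁿ:

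| Assumed q | Expected number, n = 18 | Chance, n = 18 | Chance, n = 9 |
|---|---|---|---|
| 5% | 0.9 | 60% | 37% |
| 10% | 1.8 | 85% | 61% |
| 20% | 3.6 | 98% | 87% |
| 30% | 5.4 | 99.8% | 96% |

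Eighteen is an upper limit. Section 9.1 restricts response to patients with at least three cycles, and HI needs the lineage's baseline cytopenia. The n = 9 column is purely illustrative (half of 18); there, one HI is 1/9 = 11.1 points.

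**5. Reach into the methylation data.** At the cycle 4 assessment stable disease already counts as benefit, so a misattributed HI does not change who continues. At cycle 7 only CR, PR or HI counts, so it can. The cycle 7 sample is drawn at that same visit and cannot be selected by its result. An end-of-treatment sample is scheduled for every patient. That leaves cycle 10. The primary objective concerns three cycles.

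**The case against.** The best defense is that supportive care was meant to be constant. Section 3.1 speaks of patients' existing supportive care, criterion 5 expects it to continue, and Section 6.3 does not expressly mention new starts or dose increases. That is a fair reading and a partial safeguard. But an expectation at entry is not a rule during treatment, and nothing says what happens to the response count when it is not met.

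The endpoint is also secondary, in an 18-patient pilot with no test or decision threshold attached. That limits the consequences but does not make the count interpretable.

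Four stronger readings are tempting, and the documents do not support them:

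- *Any rise in counts is a response.* Appendix 2 requires a pretreatment cytopenia, a set size of change and 8 weeks' duration. The phrase in Section 2.2 about initial counts sits awkwardly with those thresholds but does not repeal them.
- *Transfusions are as large a problem as growth factors.* New red cell transfusions work against the unit-reduction criterion, and Appendix 2 lists transfusion dependence under progression. What remains is narrow: nothing says that qualifying hemoglobin or platelet values must be free of transfusion.
- *Twelve cycles of best response widen the opportunity throughout.* Patients without CR, PR or HI after six cycles stop, so cycles 7 to 12 cannot turn a non-responder into a false responder.
- *The later methylation samples are generally selected on response.* Only cycle 10 is exposed.

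**Conclusion.** The gap is real and limited. Applied as written, Section 9.4 and Appendix 2 credit BRB with a qualifying HI that follows a started or increased erythropoietin, G-CSF or GM-CSF, or a reduction in hydrea. This biases the secondary response endpoint upwards and can influence who supplies the cycle 10 sample. It leaves the three-cycle methylation objective and the sample size untouched.

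The amount of bias cannot be estimated from the documents. The 60% to 99.8% range for at least one such HI rests on the assumed q of 5% to 30%, on 18 evaluable patients, and on independence between patients. That such starts may occur is inferred from Section 6.3 and from the absence of a prohibition; it is not stated. The point is worth correcting before analysis, but it does not threaten the trial's main question.

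**What to change.** Change the analysis only; no change to supportive care is implied. In Section 9.4, report HI in two ways:

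- HI as scored by Appendix 2.
- A BRB-attributable count. Exclude an HI in a lineage if an agent expected to raise that lineage was started or increased, or hydrea was reduced or stopped, between baseline and the end of the 8-week confirmation. Exclude it also if the hemoglobin or platelet rise rests on post-transfusion values.

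Keep the rule lineage-specific and directional. A G-CSF change should not void a platelet response, and an HI that occurs despite a reduced growth factor stays in. For each lineage, use as denominator the evaluable patients with that baseline cytopenia, and state how this fits the wording of Section 2.2.

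The cost is a few sentences. Concomitant medications and transfusion history are already collected each cycle. The documents do not say that dose is recorded, so start dates, stop dates and dose changes for these agents need to be captured. The downside is a slightly lower headline HI rate, and the restricted count may drop a genuine BRB response that coincided with a growth-factor start. Showing both counts makes that visible.

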9.5 Evaluation of Safety

The study will use the CTCAE v4.0 for reporting of adverse events. Patients will be evaluated every cycle for toxicity.

10 STATISTICAL CONSIDERATIONS

Methods for berry components (ellagic acid and anthocyanins)

A descriptive analysis will be performed for ellagic acid and anthocyanin data. Means, medians and confidence intervals will be calculated for all absolute and relative differences.

Methods for analysis of methylation changes

The primary analysis will consist of six mixed effect models with a random effect for patient, and 4 pairwise comparison of baseline methylation to each treatment times. A Bonferroni correction for 24 total comparisons will be applied to maintain a 5% experimentwise error rate. The primary outcome will be analyzed as the relative methylation rate (difference/baseline). Absolute methylation will also be analyzed, if appropriate for this data. Missing data will be assumed to be missing at random (MAR). Patients with partial data before six6 cycles, e.g., from their visits at cycle 2 or 3, will be included in the analysis.

Power calculation

Strong changes in methylation levels have been observed in pilot data, with mean differences exceeding 20% difference, with standard deviations ranging from six to eight. This study calls for comparing the methylation differences from baseline to each treatment time points, and repeated over six different genes of interest, for a total of 24 comparisons. Based on a two-sided paired *t*-test with 5% type I error rate with Bonferroni adjustment for 24 comparisons, a standard deviation of 8.0 and methylation difference of 12%, a sample size of 16 will be sufficient for 95% power. To date, seven patients were enrolled to the trial and they all finished three cycles of BRB treatment. Based on the current compliance to the treatment protocol, no one dropped and no one was noncompliant. Therefore, we assume that there will be no more than 5% non-compliance to the treatment protocol. An addition of 5% will be recruited, so power can be maintained using nonparametric methods (Wilcoxon Signed-Rank test). Therefore, this brings the final sample required sample size to 18 patients to maintain the power of the study. *Toxicity monitoring plan (stopping rule)*

Severe toxicity is not expected with BRB. As a precaution for unexpected high toxicity, the trial enrolment will be pause and the protocol reviewed if a toxicity rate exceeding 15% is observed. The following table gives the stopping rule a Pocock-type boundary for 15% toxicity rate:

# enrolled	3	5	9	12	16	18
Pause if toxicities	3	4	5	6	7	8
equal or greater than						

Ex: Five toxicities with 10 enrolled would call for a pause for review.

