2 HYPOTHESIS AND OBJECTIVES

2.1 Primary Objectives

To evaluate the potential hypomethylating effects of freeze-dried black raspberries (BRBs) in the peripheral blood of patients with myelodysplastic syndrome or myelodysplastic syndrome/ myeloproliferative neoplasms(MDS/MPN) after three cycles of BRB administration.

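### The primary endpoint is methylation after three cycles, but the primary analysis is 24 tests at four unnamed times and gives the three-cycle contrast no special role

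*Combined protocol and SAP*

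**What the plan says.** Section 2.1 (objective) and Section 3.3 (endpoint) both ask about methylation in peripheral blood "after three cycles of BRB administration". Cycles last 28 days and methylation blood is drawn before dosing on day 1, so the matching sample is C4D1.

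Section 10, under methylation changes, sets up six mixed models, each with "4 pairwise comparison of baseline methylation to each treatment times. A Bonferroni correction for 24 total comparisons will be applied". The power paragraph repeats the structure: "This study calls for comparing the methylation differences from baseline to each treatment time points, and repeated over six different genes of interest". It then gives the planning values: "a standard deviation of 8.0 and methylation difference of 12%, a sample size of 16 will be sufficient for 95% power". No time is attached to that power statement.

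The only hint at which times are meant is the missing-data sentence: "Patients with partial data before six6 cycles, e.g., from their visits at cycle 2 or 3, will be included in the analysis". In Section 10, three cycles are mentioned only in a remark on progress: "To date, seven patients were enrolled to the trial and they all finished three cycles of BRB treatment".

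Section 3.1 and Appendix 4 schedule methylation samples on day 1 of cycles 1, 2, 3, 4, 7 and 10 and at the end of treatment. The Study Calendar and Section 5.5 place that last sample 30 days after discontinuation.

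**The concern.** The endpoint asks one question at one time. The primary analysis asks the same question at four times and treats the answers as equals. If one gene passes the threshold at cycle 2 and nothing passes at C4D1, the primary analysis has produced a significant result, and the plan does not say whether the objective has been met. Nor does it say what follows if C4D1 is significant and the other times are not.

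The four times also cannot be read directly off the schedule. Testing every treatment time would give five on-treatment comparisons (C2, C3, C4, C7, C10), or six with the post-treatment sample. Four fits C2, C3, C4 and C7, and the reference to six cycles points that way, but the text does not say so. While the times are unnamed, the family can be settled after the data are seen.

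Finally, the contrast that the endpoint wants pays a multiplicity price for times it did not ask about.

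**Working it through.** **Inputs (Section 10).** Two-sided paired t-test, 5% error with Bonferroni over 24, difference 12, SD 8.0, n = 16 raised to 18, six genes. C4D1 and a family of six tests are deductions: three 28-day cycles, and six genes × one time.

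**Formula.** Power = P(|T| > c), where T is noncentral t with n − 1 degrees of freedom and noncentrality (difference/SD) × √n, and c is the 1 − α/2 quantile of the central t.

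**Reproducing the plan's figure.** α = 0.05/24 = 0.00208. At n = 16 the noncentrality is (12/8) × √16 = 6.0 and c = 3.71 on 15 df, giving power of 97.3%. Power is 93.1% at n = 14 and 95.7% at n = 15, so 15 is the minimum for 95% and the stated 16 is sufficient. Two 5% allowances give 16 × 1.05 × 1.05 = 17.6, which rounds up to the stated 18.

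**Where the error rate is spent.** Six genes × (4 − 1) other times = 18 tests, and 18 × 0.05/24 = 3.75 of the 5 percentage points. This is a minimum, because it assumes that C4D1 is one of the four times.

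**No effect at any time.** Null simulation: n = 16, times C2/C3/C4/C7, shared baseline, complete normal data, each test at 0.05/24, 200,000 runs, Monte Carlo standard error about 0.05 points.

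| | Any test significant | Some C4D1 test significant | Only other times significant |
|---|---|---|---|
| Genes independent | 4.6% | 1.2% | 3.4% |
| Gene correlation 0.5 | 4.2% | 1.1% | 3.1% |

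So about three-quarters of false-positive trials (3.4/4.6) would show nothing at the time the endpoint names.

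**Power per gene at C4D1, SD 8.** Differences below 12 are my assumption.

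| True difference | n | 24 tests (0.00208) | 6 tests (0.00833) |
|---|---|---|---|
| 12 | 16 | 97.3% | 99.6% |
| 12 | 18 | 99.1% | 99.9% |
| 10 | 16 | 86.8% | 96.1% |
| 8 | 16 | 61.6% | 81.3% |
| 6 | 16 | 29.6% | 50.6% |

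Patients needed for 95% power at difference 12: 15 with 24 tests, 12 with six. Difference detectable at n = 16 with 95% power: 11.3 with 24 tests, 9.7 with six.

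**If all five on-treatment times were tested at 0.05/24.** There would be 30 tests, and the Bonferroni bound would be 30 × 0.05/24 = 6.25%. The text makes this reading unlikely.

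**The case against.** The strongest reply is that nothing numerical breaks. Bonferroni over 24 holds the error rate of the stated family at 5%, a C4D1 test inside it is judged more strictly rather than less, and 16 and 18 patients are enough on either count. At the planning values the loss is 2.2 power points at n = 16 and 0.8 at n = 18. The larger losses need true differences of 6 to 10, whereas Section 10 cites pilot differences above 20 and already plans on 12. All of this is right. The smaller differences show sensitivity, not a shortfall in the plan.

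It is also fair that 24 is coherent for C2, C3, C4 and C7, and that this is probably what was meant. The 30-test case should carry little weight.

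A third point concerns the remedy. Moving to six tests relaxes the threshold fourfold at a time that seven patients had already reached, in a single-group study. That risk is real. Section 9.3 says "The research samples will be batched", but the documents do not say whether any have been assayed. The change therefore has to be dated and any sight of results disclosed.

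None of this supplies the missing link between 24 results and a one-time endpoint. Calling the study a pilot does not remove the need for it, since the plan itself claims a 5% experimentwise error rate and 95% power.

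**Conclusion.** The concern holds and should be fixed. The primary endpoint and the primary analysis address different sets of times, and no rule connects them. The main harm is in interpretation: at least 18 of 24 primary tests lie outside the endpoint, and a positive result at any of them has no defined meaning for the objective. The power cost is small at the planning values and material only if the true change is well below 12. Type I error over the four-time family is not inflated, and the sample size does not need to change.

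The calculations rest on the paired t-test that the protocol uses for its own power. The mixed model, with data missing at random, could give somewhat different figures. Confidence is high on the mismatch and the unnamed times, and low that more than 24 tests are intended.

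**What to change.** Amend Section 10 before any methylation analysis:

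- Make C4D1 versus C1D1 in the six genes the primary analysis, with Holm or Bonferroni over six tests. The contrast can still come from the planned mixed models using all visits.
- State that the 95% power refers to C4D1.
- Report the other times as secondary, with confidence intervals. Label C10 as responder-selected, because continuing past the cycle 7 assessment requires a response, and label the last sample as off treatment.
- If several times must stay in the primary family, name them, set the divisor to the actual count (24 for C2/C3/C4/C7, 30 with C10 added), and say how the results answer the three-cycle objective.
- Record the date of the change and that it came before the methylation data were analysed. If some results have been seen, say so and report both the 6-test and the 24-test results.

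Fixing the six-test family also means settling which six genes it contains; Section 9.3 says only "The identified genes will be validated using pyrosequencing".

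**Cost.** No extra patients, samples or assays, and 18 patients stand. It needs a protocol amendment with IRB approval (Section 12.3), made mid-trial. The trade-off is that an effect seen only at C2, C3, C7 or C10 becomes a secondary finding.

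### Holm's step-down on the same 24 methylation tests would hold the same 5% experimentwise error as the planned Bonferroni and never reject less: a cheap refinement, not an error

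*Combined protocol and SAP*

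**What the plan says.** Under Methods for analysis of methylation changes, Section 10 defines the primary analysis as "six mixed effect models with a random effect for patient, and 4 pairwise comparison of baseline methylation to each treatment times". The adjustment is single-step: "A Bonferroni correction for 24 total comparisons will be applied to maintain a 5% experimentwise error rate". No step-down, gatekeeping or other multiplicity procedure is named.

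The Power calculation paragraph uses the same family, "repeated over six different genes of interest, for a total of 24 comparisons", and sizes the trial on a two-sided paired *t*-"test with 5% type I error rate with Bonferroni adjustment for 24 comparisons". With "a standard deviation of 8.0 and methylation difference of 12" percent, it concludes that "a sample size of 16 will be sufficient for 95% power", and then raises the number to 18. The pilot data are described "with mean differences exceeding 20% difference, with standard deviations ranging from six to eight".

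**The concern.** The stated aim is a 5% experimentwise error rate; Bonferroni is only the means. Single-step Bonferroni holds every contrast to 0.05/24 however many of the others have already been rejected. Holm relaxes the threshold after each rejection and needs no assumption about how visits and genes are correlated. That matters here, because the four contrasts for a gene share one baseline. In an 18-patient trial, power that can be had without loosening error control is worth considering. At stake is the chance of confirming the weaker contrasts, for example at a visit where the change is smaller or fewer patients remain.

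**Working it through.** **Inputs from Section 10.** Difference 12; SD 8.0, read as the SD of the paired difference; two-sided test; 24 comparisons; n = 16 raised to 18; pilot differences above 20 with SD 6 to 8.

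**Step 1: reproduce the plan's figure.** Alpha per test = 0.05/24 = 0.00208. Standardised difference = 12/8 = 1.5. Power comes from the noncentral *t* distribution with noncentrality 1.5 × √n:

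| n | Noncentrality | Critical t | Power |
|---|---|---|---|
| 15 | 5.81 | 3.767 | 95.7% |
| 16 | 6.00 | 3.713 | 97.3% |
| 18 | 6.36 | 3.627 | 99.1% |

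So 16 is sufficient for 95% power. The increase also reproduces: 16 × 1.10 = 17.6 and 16/0.95/0.95 = 17.7, both rounding up to 18.

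**Step 2: Holm never rejects less.** Order the p-values from smallest to largest and reject the k-th as long as it and all smaller ones satisfy p(j) ≤ 0.05/(24 − j + 1). The thresholds run from 0.05/24 = 0.00208 at k = 1, through 0.05/12 = 0.00417 at k = 13, to 0.05 at k = 24. Each is at or above 0.05/24. A p-value that passes Bonferroni, and every smaller one, therefore passes Holm.

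**Step 3: Holm holds 5% under any dependence.** Suppose m0 of the 24 null hypotheses are true. The first false rejection comes at step 24 − m0 + 1 or earlier, where the threshold is at most 0.05/m0. A false rejection thus requires some true-null p-value at or below 0.05/m0. By the union bound this has probability at most m0 × 0.05/m0 = 5%. Correlation does not enter.

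**Step 4: size of the gain.** Simulation of 24 paired *t*-tests (6 genes × 4 times), SD 8, n = 18, 10,000 trials per scenario. The documents give no correlations between change scores, so three (time, gene) pairs were assumed: (0, 0), (0.5, 0.3) and (0.8, 0.6). The numbers of real effects and the 8-point change are also assumptions. Ranges are over the correlations.

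| True change | Real effects | Bonferroni, per real effect | Holm, per real effect |
|---|---|---|---|
| 20 | 24 | 100% | 100% |
| 12 | 24 | 99.0–99.1% | about 100% |
| 12 | 12 | 99.0–99.1% | 99.5–99.6% |
| 12 | 4 | 98.9–99.0% | 99.1–99.2% |
| 8 | 24 | about 72% | 87–93% (90% at the middle correlations) |
| 8 | 12 | about 72% | 76–78% |
| 8 | 6 | about 72% | 73–74% |

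**Step 5: what does not change.** Holm's first threshold is Bonferroni's threshold, so the event of at least one rejection among the 24 is the same under both. With no real effects, the simulated experimentwise error at n = 18 was identical for both methods, at 3.3–4.9%. With some effects real, Holm's error was at most 5.1%, within simulation error of 5% (standard error about 0.2 points). In no simulated trial did Bonferroni reject a hypothesis that Holm retained.

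**The case against.** The strongest reply is that nothing is broken. Bonferroni is pre-specified, valid and used consistently in both the analysis and the sizing, and power at the design values is already 97–99%. All of that stands.

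Two stronger readings are tempting, and the documents support neither.

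- A reader might infer that real methylation changes will be missed with 18 patients. At the planned effect Bonferroni already detects each one with 99.1% probability, and at the pilot effect there is nothing left to gain. Holm profits from the number of real effects, not from large ones.
- A reader might point to the chance of detecting all 24 effects, which at n = 16 and 12 points rises from 53–78% to 99.5–99.8% over the assumed correlations. The protocol sets no such success criterion. Sections 2.1 and 3.3 frame the primary question as the effect after three cycles.

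Three further objections stand in part. The simulation uses complete-data paired tests, whereas the plan specifies mixed models on relative change with partial data included; Steps 2 and 3 carry over to any valid p-values, but the percentages may not. Matching simultaneous intervals are simple under Bonferroni and not under Holm. Finally, Section 10 records that seven patients had already finished three cycles, so this would be a change made during the trial.

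On the other side, the protocol gives reasons why some contrasts could be weaker than 12 points or rest on fewer patients. Section 1 attributes the colon effect mainly to local action and suggests that effects accumulate with time. Section 3.1 makes continued treatment conditional on tolerance and benefit.

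**Conclusion.** This is a free or cheap improvement and not a flaw in the plan. Holm's equal error control and its dominance over Bonferroni are mathematical facts and need no assumption about correlation. The size of the gain does depend on assumptions. With 18 patients and SD 8 it is under one point per comparison at 12 points and zero at 20 points. At an assumed 8 points it ranges from about 2 points with six real effects to about 18 points with all 24 real (72% to 90% at the middle correlations). It becomes material only if many effects are real and some are smaller than planned or some visits have fewer patients.

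The power figures also read the SD of 8.0 as that of the paired difference. Were it a per-visit SD, Bonferroni power at n = 16 would be 69% at a within-patient correlation of 0, 85% at 0.25 and 97.3% at 0.5. That would make Holm more useful without changing the conclusion.

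**What to change.** In Section 10, Methods for analysis of methylation changes, replace *Bonferroni correction* with *Holm step-down procedure* for the same 24 comparisons. Leave the Bonferroni-based Power calculation paragraph unchanged and say there that it is conservative for the Holm analysis; 18 patients remains adequate on the plan's own assumptions. Date the amendment before any methylation data are analysed.

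If Bonferroni simultaneous intervals are reported beside the Holm tests, state in advance that a Holm-significant contrast may have an interval that includes zero. The cost is a short text change and that less tidy link between tests and intervals. No extra patients, samples or modelling assumptions are needed.
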